16.34 Analysis of Patient-Reported Outcomes (Quality of Life and Symptoms)

Patient-reported outcomes (quality of life and symptoms) will be assessed prior to review of treatment response and discussions of patient's general health since last treatment evaluation. Patient-reported outcomes will include the EORTC QLQ-C30, a 30-item patient-reported questionnaire about patient ability to function, symptoms related to the cancer and its treatment, overall health and quality of life, and perceived financial impact of the cancer and its treatment. 28 of the 30 items are measured on a 1-4 scale (1=not at all; 4=very much) with the remaining two items (overall health and overall quality of life) scored on a 1-7 numeric analogue scale (1=very poor; 7=excellent). The recall period for the EORTC QLQ-C30 is one week. The EORTC QLQ-C30 is the product of more than a decade of collaborative research and to date, more than 2200 studies using the EORTC QLQ-C30 have been registered with the EORTC (Fayers et al, 2001 [EORTC Scoring Manual]). In addition, patients will complete the newly developed EORTC QLQ-BIL21. This EORTC module assessed quality of life domains specific to biliary cancers using 21 items on the same 1-4 scale as the core questionnaire. This questionnaire is in the process of being validated (data from this study may be used to provide validation information). Skin and bowel symptoms will be assessed using the Skindex-16 and Bowel Function Questionnaire (BFQ). The Skindex-16 contains 16 questions each on a 0-10 scale (0=never bothered, 10=always bothered) assessing skins problems and has previously been validated (Chren et al, 2001). The BFQ, developed and created by Mayo Clinic physicians, identifies patient-reported problems with various aspects of bowel function (yes or no response) to help evaluate how bowel dysfunction affects normal activities and quality of life (QOL). Content validity of this instrument has been previously reported (Atherton et al, 2013). We will use the Uniscale assessment of overall quality of life (Sloan, O'Fallon et al, 1998) on a scale of 0-10 (0=as bad as it can be, 10=as good as it can be). This single item is one of the most widely used quality of life measures and has been shown to be prognostic for survival above and beyond performance status and other common prognostic factors in a range of cancer types. The Was It Worth It (WIWI) questionnaire is minimalist and efficient, asking only five key questions with trichotomous responses about the patient's satisfaction with the study and likelihood of recommending it to other patients. This tool has been pilot tested in a recent clinical trial looking at the QOL of patients participating in phase I clinical trials at Mayo Clinic Rochester and has demonstrated to be easy to complete, understandable, and important to patients. It has also been used to assess patient satisfaction as a companion protocol (N0392) to North Central Cancer Treatment Group cancer treatment phase II and III clinical trials.

A paper booklet containing all the patient-reported outcomes will be administered in clinic at baseline and every cycle, and each PRO will be scored according to the published scoring algorithm. Scale score trajectories over time will be examined using stream plots and mean plots with standard deviation error bars overall. Changes from baseline at each cycle will be statistically tested using paired t-tests, and standardized response means (mean of the change from

baseline scores at a given cycle, divided by the standard deviation of the change scores) will be interpreted (after applying Middel's (2002) adjustment) using Cohen's (1988) cut-offs: <0.20 = trivial; $0.20-0.50$ = small; $0.50-0.80$ = moderate; and ≥ 0.80 = large. Correlation between outcomes will employ Pearson and/or Spearman correlations at individual time points.

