4.0 Test Schedule

Cycle = 28 days

Tests and procedures	Active Monitoring Phase						
	≤14 days prior to registration	Cycle 1 Day 1 (± 2 days) prior to treatment	Cycle 1 Days 8, 15, 22 prior to treatment	Cycle 2 and beyond Day 1 (± 2 days) prior to treatment	Q 8 weeks from Cycle 1 Day 1 (± 5 days)	Every 3 Cycles starting at end of Cycle 3 (± 5 days)	End of treatment
History and exam, wt, ECOG	X			X			X
Height, Child Pugh score	X						
Vitals ³	X	X	X	X			X
Hematology group WBC, ANC, Hgb, PLT	X	X	X	X			X
Chemistry group Sodium, potassium, chloride, bicarbonate, total protein, albumin, calcium, glucose, BUN, total bilirubin, creatinine, alkaline phosphatase, SGOT (AST), SGPT (ALT)	X	X		X			X
Amylase ^R	X	X	X	X			
Lipase ^R	X	X	X	X			
CA19-9		X		X ⁵			
EKG ^R	X					X	
Echocardiogram	X			X ¹⁰			
Tumor measurement and Imaging (CT or MRI as clinically)	X ¹				X ²		

indicated)							
Pregnancy test	X ⁴						
Patient questionnaire booklet	X ⁹			X ⁹			
Adverse event assessment	X		X	X			
Research Archival Tissue (optional)	X ⁸						
Research Tissue Biopsy (optional)				X ^{7,R}			X ⁶
Research blood samples (Optional)	X			X			X

1. Imaging studies such as CT scans, and MRIs can be performed ≤ 28 days prior to registration. Use same imaging throughout the study. Assessment by physical exam should be done ≤ 14 days prior to registration.
 2. Tumor assessment must be performed at least every 8 weeks. Tumor assessment should be performed at any time during the treatment cycle that disease progression is clinically suspected so that patient can go off treatment and receive other therapy.
 3. Includes weight, blood pressure, pulse and temperature
 4. Women of childbearing potential only. Must be done ≤ 7 days prior to registration.
 5. Only to be collected if $> \text{ULN}$ on Cycle 1 Day 1
 6. If patient has experienced disease progression and at such time a standard of care biopsy is ordered by the treating physician, waste specimen will be collected, fresh frozen and stored for future correlative studies. Perform only if archival specimen was available.
 7. Perform only if archival specimen was available.
 8. Archival FFPE and/or fresh frozen tissue collected in setting of standard of care procedures.
 9. Patient questionnaire booklet must be used; copies are not acceptable for this submission. Booklet should be completed by patient prior to review of treatment response and discussions of patient's general health since last treatment evaluation.

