6.4 An optional correlative research component is part of this study, there will be an option to select if the patient is to be registered onto this component (see Sections 14.0 and 17.0).

- Patient has/has not given permission to have a tissue biopsy at cycle 2, day 1.
 - Patient has/has not given permission to allow any excess tissue collected while on this study to be used for research studies
 - Patient has/has not given permission for blood collection at screening, Prior to each cycle, and at end of study to be used for research studies.
- 6.5 At the time of registration, the following will be recorded:
- Patient has/has not given permission for his/her tissue and blood sample(s) to be stored and used in future research of biliary cancer at Mayo Clinic
 - Patient has/has not given permission for his/her tissue and blood sample(s) to be stored and used in future research at Mayo Clinic to learn about, prevent, or treat any other health problems
 - Patient has/has not given permission for Mayo Clinic to give his/her tissue and blood sample(s) to researchers at other institutions
- 6.6 Treatment cannot begin prior to registration and must begin ≤ 7 days after registration.
- 6.7 Pretreatment tests/procedures (see Section 4.0) must be completed within the guidelines specified on the test schedule.
- 6.8 All required baseline symptoms (see Section 10.6) must be documented and graded.
- 6.9a Treatment on this protocol must commence at a Mayo Clinic institution under the supervision of a medical oncologist.
- 6.9b Study drug is available on site.
- 6.9c Patient questionnaire booklet is available on site; copies are not acceptable for this submission.

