Other Non-Hematologic events	≥ Grade 3	Ponatinib	Omit drug and follow patient at least weekly until adverse event has resolved to grade ≤ 2, restart agent at next lower dose level. See sections 8.41 through 8.47 for guidance on other non-hematologic events

* Located at http://ctep.cancer.gov/protocolDevelopment/electronic_applications.ctc.htm

** Use the following to describe actions in the Action column:

- Omit = Treatment is not given for the day/days that are omitted and will not be made up, but treatment may resume once the adverse event has resolved as mandated in Table 8.2. For example, if treatment is omitted on Day 8, but the adverse event has resolved by Day 15, treatment may resume on Day 15.
- Hold/Delay = Treatment can be made up as part of this cycle
- Discontinue = Treatment is totally stopped

NOTE: If the patient experiences a significant adverse event requiring a dose reduction at the start of the next cycle, then the dose will remain lowered for that entire subsequent cycle. If that cycle is completed with no further adverse events >Grade 2, then the dose may be increased, at the investigator's discretion, one level at a time, in the following cycles.

NOTE: Adverse events requiring a dose-reduction step for any or all drugs beyond the two dose-reduction steps (levels -1 and -2) will be at the discretion of the treating physician, if the decision is made for the patient to be kept on study. These dose reductions must be clearly recorded in reported clinical data.

- 8.3 A new course of treatment may begin on the scheduled Day 1 of a new cycle if:
- The ANC is $\geq 1500/\mu\text{L}$;
 - The platelet count is $\geq 75,000/\mu\text{L}$;
 - Any other Ponatinib related adverse event that may have occurred has resolved to \leq Grade 1 or baseline severity.

If these conditions are not met on scheduled Day 1 of a new cycle, the subject will be evaluated at least weekly and the new cycle of treatment will not be initiated until the adverse event has resolved as described above.

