When therapy is resumed it will be considered day one of this new cycle. If Ponatinib was halted during the previous cycle and was restarted with a one-level dose reduction without requiring an interruption for the remainder of the cycle, then that reduced dose level will be initiated on Day 1 of the new cycle. **If ponatinib was omitted for the remainder of the previous cycle or if the new cycle is delayed due to adverse event newly encountered on the scheduled Day 1**, then the scheduled cycle will be started with a one-level dose reduction. If the study drug cannot be restarted within 28 days of the

scheduled Day 1 of a given cycle, the patient will be removed from study treatment and will proceed to event monitoring.

8.4 Additional adverse event guidance:

8.41 Hepatotoxicity: Iclusig can cause hepatotoxicity, including liver failure and death. Fulminant hepatic failure leading to death occurred in an Iclusig-treated patient within one week of starting Iclusig. Two additional fatal cases of acute liver failure also occurred. The fatal cases occurred in patients with blast phase CML (BP-CML) or Philadelphia chromosome positive acute lymphoblastic leukemia (Ph+ ALL). Severe hepatotoxicity occurred in all disease cohorts. Iclusig treatment may result in elevation in ALT, AST, or both. Monitor liver function tests at baseline, then at least monthly or as clinically indicated. Interrupt, reduce, or discontinue Iclusig as clinically indicated.

8.42 Pancreatitis: Clinical pancreatitis occurred in 6% (28/449) of patients (5%, grade 3) treated with Iclusig. Pancreatitis resulted in discontinuation or treatment interruption in 6% of patients (25/449). The incidence of treatment-emergent lipase elevation was 41%. Check serum lipase every 2 weeks for the first 2 months and then monthly thereafter or as clinically indicated. Consider additional serum lipase monitoring in patients with a history of pancreatitis or alcohol abuse. Dose interruption or reduction may be required. In cases where lipase elevations are accompanied by abdominal symptoms, interrupt treatment with Iclusig and evaluate patients for pancreatitis. Do not consider restarting Iclusig until patients have complete resolution of symptoms and lipase levels are less than 1.5 x ULN.

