18.0 Records and Data Collection Procedures

18.1 Submission Timetable

Initial Material(s)

CRF	Active-Monitoring Phase (Compliance with Test Schedule Section 4.0)
On-Study	≤14 days after registration
Adverse Event - Baseline	
RECIST Measurement – Baseline	
Concomitant Medication - Baseline	
Hematology Laboratory	
Chemistry Laboratory	
Other Laboratory	
Patient Questionnaire Booklet ¹	
Booklet Compliance ²	
OP and Path Reports (see Section 17.0)	
Research Blood Submission	≤30 days after registration
Research Tissue Submission	
End of Active Treatment/Cancel Notification	Submit ≤2 weeks after registration if withdrawal/refusal occurs prior to beginning protocol therapy

1. Patient questionnaire booklet **must** be used; copies are not acceptable for this submission.
2. This form must be completed only if the patient questionnaire booklet contains absolutely NO patient provided assessment information.

Test Schedule Material(s)

CRF	Active-Monitoring Phase (Compliance with Test Schedule Section 4.0)
	At each evaluation during treatment
Evaluation/Treatment	X ¹
Adverse Event	X

CRF	Active-Monitoring Phase (Compliance with Test Schedule Section 4.0)
	At each evaluation during treatment
RECIST Measurement	X
Concomitant Medication	X
Other Laboratory	X (see Section 4.0)
Hematology Laboratory	X (see Section 4.0)
Chemistry Laboratory	X (see Section 4.0)
Research Tissue Submission	X (see Section 17.0)
Research Blood Submission	X (see Section 14.0)
Patient Questionnaire Booklet	X ²
Booklet Compliance	X ³
End of Active Treatment/Cancel Notification	X
Notification Form – Grade 4 or 5 Non-AER Reportable Events/Hospitalization	At each occurrence (see Section 10.0)
ADR/AER	At each occurrence (see Section 10.0)

1. Complete at each evaluation during Active Treatment (see Section 4.0).
2. Patient questionnaire booklet **must** be used; copies are not acceptable for this submission. To be completed prior to treatment every cycle.
3. This form must be completed only if the patient questionnaire booklet contains absolutely NO patient provided assessment information.

Follow-up Material(s)

CRF	Event Monitoring Phase ¹				
	q. 6 months until PD	At PD	After PD q. 6 mos.	Death	New Primary
Event Monitoring	X ²	X ²	X	X	At each occurrence

1. If a patient is still alive 2 years after registration, no further follow-up is required.
2. Submit copy of documentation of response or progression to the MCCC Operations Office, Attention: XXXXXXXXXX.

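### The baseline quality-of-life booklet can precede the first dose by up to 21 days, and the plan does not say which visit carries a later booklet when toxicity delays a cycle

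*Combined protocol and SAP*

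**What the plan says.** **Frequency.** Section 16.34 says: "A paper booklet containing all the patient-reported outcomes will be administered in clinic at baseline and every cycle".

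**Baseline.** The Section 4.0 booklet row has a mark in the screening column, headed "≤14 days prior to registration", and none under Cycle 1 Day 1. Section 6.6 adds: "Treatment cannot begin prior to registration and must begin ≤ 7 days after registration".

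**Later booklets.** The next mark in Section 4.0 is in the column "Cycle 2 and beyond Day 1 (± 2 days) prior to treatment". In Section 18.1 a footnote to the on-treatment booklet reads "To be completed prior to treatment every cycle", and the column above it covers each evaluation during treatment. Footnote 9 of Section 4.0 wants the booklet filled in before response and general health are discussed.

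**Delays.** Under Section 8.3 a cycle may start if neutrophils and platelets are adequate and other ponatinib-related events are at Grade 1 or less, or at baseline. Otherwise the patient is evaluated at least weekly and "the new cycle of treatment will not be initiated until the adverse event has resolved as described above". Section 8.3 then says: "When therapy is resumed it will be considered day one of this new cycle". A restart may come up to 28 days after the scheduled Day 1; beyond that the patient leaves study treatment.

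**Analysis.** In Section 16.34, change from baseline at each cycle is tested with paired t-tests, and standardized response means are labelled from trivial to large. The same section says: "The recall period for the EORTC QLQ-C30 is one week". The forms in Appendices V, VI and VIII also ask about the past week. Section 2.33 gives the aim as description, under translational and correlative research.

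**The concern.** A change-from-baseline analysis needs a baseline close to the first dose and follow-up at times that do not depend on the outcome. The schedule secures neither.

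Patients here have advanced, refractory disease and may change between screening and first dose. With an early baseline, that pre-dose change enters the paired difference as if it had occurred on ponatinib.

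The second problem is the moving Day 1. If the booklet moves with it, the patients whose toxicity holds up a cycle report later, after recovery, about a week with little or no drug. The battery includes skin and bowel questionnaires, and Section 15.17 lists rash and diarrhea among effects in more than 10% of patients, so the symptoms of interest can themselves shift the assessment. Patients under one cycle number would also be at different times since first dose. A toxicity-week score that was never collected cannot be recovered in the analysis.

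**Working it through.** **1. Stated figure.** The documents give no sample size, power or effect size for the patient-reported outcomes, so there is nothing of the plan's own to reproduce. The check rests on the visit windows.

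**2. Baseline lead.**
- Screening to registration: 0 to 14 days (Section 4.0).
- Registration to first dose: 0 to 7 days (Section 6.6).
- Longest lead: 14 + 7 = **21 days**. Shortest: 0 days.

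**3. Interval from baseline to the Cycle 2 booklet** (28-day cycle, ± 2 days).

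| Case | Arithmetic | Days |
|---|---|---|
| Shortest | 0 + 28 − 2 | 26 |
| Longest, no delay | 21 + 28 + 2 | 51 |
| Longest delay, booklet on the moved Day 1 | 21 + 28 + 28 | 77 |
| Baseline pre-dose on Cycle 1 Day 1, next booklet on scheduled Day 1 | 28 ± 2 | 26 to 30 |

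At the longest lead with an on-time Cycle 2 booklet, 21 / (21 + 28) = 43% of the interval precedes any drug. This is the extreme of both windows, not a typical value.

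**4. Recall week after a delay of D days, booklet completed on the moved Day 1.** No ponatinib is given while the new cycle waits, so the off-drug share of a seven-day recall is at least min(D, 7) / 7:
- D = 3: 3/7 = 43%.
- D = 7 to 28: 100%.

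If the moved Day 1 also governs the ± 2 day window, then from D = 3 onward a booklet completed on the scheduled day is out of window.

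**5. The two readings.**
- *Moved Day 1:* the booklet belongs to Day 1 before treatment, and Section 8.3 makes the resumption date Day 1.
- *Scheduled Day 1:* Section 8.3 judges readiness on the scheduled day. The examination, blood tests and adverse event assessment that inform it share the booklet's column in Section 4.0, and the booklet comes before the discussion of general health.

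Neither reading is ruled out, and no section says which score stands for the cycle if both are collected.

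**6. Illustration of attenuation under the moved-Day-1 reading.** All inputs are assumptions: *d* is the share of patients delayed, *k* the true change in delayed patients relative to the others, and *ρ* the share of that change still reported after recovery.

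Observed / true = [(1 − d) + d·k·ρ] / [(1 − d) + d·k]

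- d = 0.10, k = 1, ρ = 0.75: (0.90 + 0.075) / 1.00 = 0.98.
- d = 0.20, k = 2, ρ = 0.5: (0.80 + 0.20) / 1.20 = 0.83.
- d = 0.40, k = 2, ρ = 0: 0.60 / 1.40 = 0.43.
- Booklet on scheduled Day 1 (ρ = 1): 1.00.

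**The case against.** The strongest reply is that the natural workflow already avoids the second bias: the patient attends on scheduled Day 1, fills in the booklet, and only then is readiness decided. Section 18.1's heading for each evaluation during treatment fits this. The reply stands to this extent: a reader might infer that the plan makes booklets fall due only once toxicity has resolved, and no section says so. The threshold is also Grade 1 or baseline, not absence of symptoms, and low counts alone can delay a cycle with nothing for the patient to report. What remains is an ambiguity that sites may settle differently.

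A reader might also see a contradiction between the missing Cycle 1 Day 1 mark in Section 4.0 and the every-cycle wording of Sections 16.34 and 18.1. That is weak: Section 18.1 lists the first booklet with the initial materials, so the screening booklet can serve for Cycle 1. It does not shorten the 21 days.

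The analysis is descriptive, in one arm, and toxicity is graded separately by CTCAE, including on Cycle 1 Days 8, 15 and 22. This limits the consequences and stands. Description still needs comparable timing, and Section 16.34 does attach tests and size labels to the changes.

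Finally, no schedule of one booklet per cycle captures every toxic week. Drug can be omitted mid-cycle, as in the Day 8 to Day 15 example after Table 8.2, and a one-week recall at the next Day 1 misses it. That limit also applies to the fix below.

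**Conclusion.** Two points hold. The baseline can be up to 21 days before the first dose, which follows directly from the windows. The visit that carries a later booklet during a delay is unspecified; on one permitted reading the recall is wholly off drug from a 7-day delay onward, and symptom burden can be understated.

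It would go too far to say that ponatinib's effect on symptoms *is* mis-measured, or by a given amount. Multiplying assumed delay shares of 10%, 30% or 50% by an assumed 20-point difference gives 2, 6 or 10 points, but neither input is in the documents. The range 0.43 to 1.00 in the working is equally conditional on its assumptions. The two mechanisms can oppose each other: late booklets would understate harm, while worsening before the first dose would be charged to the drug. Only delayed patients are exposed to the second mechanism, because dosing is continuous and an on-time patient reports while on drug. Even perfect timing would not identify a causal effect in a single arm.

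The primary endpoint, the two-stage rule and the adverse event stopping rule are untouched. The change is worth making because it is cheap and removes an avoidable source of distortion.

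**What to change.** In Sections 4.0, 16.34 and 18.1:

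1. Give the baseline booklet at the existing Cycle 1 Day 1 visit, before the first dose. Appendix VIII already tells patients who have not started treatment where to stop, so the form suits this.
2. Give each later booklet at the originally scheduled Day 1 visit, before readiness is decided and whether or not the cycle starts that day. State that this booklet is the cycle's score.
3. Record the completion date and whether the patient was on or off drug. The latter matters because drug may already have been omitted late in the preceding cycle.
4. Add a sensitivity analysis by time since first dose.

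A fixed 28-day grid from Cycle 1 Day 1 is less practical. After a 14-day delay Cycle 2 starts on day 1 + 28 + 14 = 43, and the grid date of day 57 is Cycle 2 Day 15, for which Section 4.0 has no visit. Using the scheduled Day 1 needs no added visit.

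**Cost.** Schedule and analysis wording, plus the recording in item 3. Sites must hand out the first booklet before dosing on Cycle 1 Day 1, and a booklet may precede the actual start of its cycle. No dosing or delay rule changes.

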Appendix VIII
Uniscale

Please circle the number (0-10) best reflecting your response to the following that describes your feelings **during the past week, including today.**

1. **How would you describe your overall Quality of Life?**

0	1	2	3	4	5	6	7	8	9	10
As bad as										As good as
it can be										it can be

**If you have not started treatment on this study,
please stop here. Thank you for taking the
time to help us.**

**If you have started treatment on this study,
please continue to the next page.**

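### No questionnaire booklet is scheduled at End of treatment, so patient-reported state at discontinuation is not systematically captured and later-cycle changes are open to informative dropout

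*Combined protocol and SAP*

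**What the plan says.** Three sections set the timing, and they agree.

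- **Section 16.34** puts every instrument into one booklet ("A paper booklet containing all the patient-reported outcomes"), which is "administered in clinic at baseline and every cycle".
- **Section 4.0**, row "Patient questionnaire booklet", is marked in the screening column and in the column for Day 1 of Cycle 2 onward. The End of treatment cell is empty, although history and exam, vitals, hematology and chemistry are all marked there. Footnote 9 adds: "Booklet should be completed by patient prior to review of treatment response".
- **Section 18.1** lists the booklet among the forms for evaluations during treatment, with the footnote "To be completed prior to treatment every cycle". The follow-up table for the event monitoring phase lists only the Event Monitoring form. Sections 13.2 and 13.3 move patients into that phase after progression or after stopping for other reasons.

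On Was It Worth It, the Uniscale page (Appendix VIII) ends the booklet for one group ("If you have not started treatment on this study") and sends the other group to the next page ("If you have started treatment on this study"). Was It Worth It is the next appendix in the contents list.

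The analysis in 16.34 consists of stream plots, mean plots, a paired t-test of change from baseline at each cycle, and standardized response means. It gives no approach to missing booklets or dropout. It does not say which of a patient's several Was It Worth It answers is summarised.

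**The concern.** The visit at which treatment ends is where toxicity or progression is most likely to show in what a patient reports, and no booklet is scheduled there. Whether a report is missing then depends on how the patient is doing. Each paired test uses only patients who have a booklet at that cycle, so the group shrinks and becomes more selected from cycle to cycle, and means at later cycles would tend to look better than the experience of all treated patients. The same applies to Was It Worth It, which asks for a judgement that is most informative once treatment is over. It also appears to have no baseline value, so the change-from-baseline analysis cannot be applied to it.

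What is at stake is goal 2.33, the description of quality of life and symptoms. A report not collected at the stopping visit cannot be recovered later.

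**Working it through.** **1. The plan's own figures.** The documents give no sample-size or attrition figure for the PROs. The only design figures are in the Section 16.24 table. With 10 patients in Stage 1, 17 more in Stage 2, continuation on at least 1 success and a positive result on at least 3 of 27, the exact binomial sum over x = 1 to 10 of P(X1 = x) × P(X2 ≥ 3 − x) gives 0.1204, 0.4324, 0.6980, 0.8541 and 0.9322 at true rates 0.05 to 0.25. The table has 0.12, 0.43, 0.70, 0.85 and 0.93, so it reproduces. Nothing in this point changes it.

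**2. What the schedule yields, by time of leaving.**

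| Patient leaves treatment | On-treatment booklet | Was It Worth It (inferred) | Report after the event that ended treatment |
|---|---|---|---|
| Before Cycle 2 Day 1 | None | None | None scheduled |
| Mid-cycle, after Cycle 2 Day 1 | At least one | Yes, from the last Day 1 visit | None scheduled |
| At a Day 1 visit, Cycle 2 or later | All earlier ones, possibly that day's | Possibly that day's | Possible, because the booklet precedes the response review |

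The third row is uncertain. The 18.1 footnote ties the booklet to the time before treatment in each cycle and can be read as leaving out a patient who will not be dosed that day.

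**3. When exits can occur.** Scans are every 8 weeks = 56 days = 2 × 28, so they fall near Day 1 of Cycles 3, 5 and so on. A planned scan cannot by itself end treatment in Cycle 1. Toxicity can end it at any time: Table 8.2 calls for discontinuation for stroke, myocardial infarction and thromboembolic events, among others. Section 9.4 reports vascular occlusion in at least 27% of patients in earlier trials, with onset possible within 2 weeks of starting. The mid-cycle route is therefore real, but its rate in this population is not given.

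**4. Size, by assumption only.** Let d be the share stopping before Cycle 2 Day 1. The number with no on-treatment PRO is 27 × d: 27 × 0.10 = 2.7 and 27 × 0.20 = 5.4, or about 3 to 5 patients.

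A wider illustration assumes a constant rate of leaving treatment. If p is the share still on treatment at 16 weeks (Cycle 5 Day 1, 4 × 28 days), the share on treatment after k cycles is p^(k/4). The values 0.05 and 0.20 borrow the design's null and target rates; 0.40 and 0.50 are more favourable cases. Everyone still on treatment is taken to complete the booklet.

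| p | Booklet at Cycle 2 Day 1, 27 × p^(1/4) | Booklet at Cycle 5 Day 1, 27 × p | Off before Cycle 2 Day 1 | Off before Cycle 5 Day 1 with at least one on-treatment booklet |
|---|---|---|---|---|
| 0.05 | 12.8 | 1.4 | 14.2 | 11.4 |
| 0.20 | 18.1 | 5.4 | 8.9 | 12.7 |
| 0.40 | 21.5 | 10.8 | 5.5 | 10.7 |
| 0.50 | 22.7 | 13.5 | 4.3 | 9.2 |

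The constant rate probably overstates loss in Cycle 1, because the first planned scan is at 8 weeks. The table shows how far the paired-test denominator could fall by Cycle 5. It also shows that many early leavers would still have at least one on-treatment booklet.

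**The case against.** The empty cell is not in dispute. The case on the other side is about how much follows from it, and much of that case stands.

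- A reader might infer that patients who stop early never answer the satisfaction questions. The documents do not support this. Every booklet holds all the instruments, and anyone who has started treatment is sent past the Uniscale page, so Was It Worth It appears to be asked from Cycle 2 Day 1 on. Only patients off before then miss it. The Appendix IX text is not in the copy read, so even this timing is an inference.
- A reader might infer that every patient lacks a report at the point of stopping. That is too absolute. Footnote 9 puts the booklet before the response review, so a patient found to have progressed at a Day 1 visit may already have completed one.
- A reader might infer that the PRO results describe only patients doing well. The baseline and the Cycle 2 and 3 booklets include patients who later progress. Selection grows with time; it does not define the whole dataset.
- The PRO goal is descriptive and listed under correlative research. There is no comparator arm, and no stopping rule or primary or secondary endpoint uses these data.
- An extra booklet at varying times would not enter the by-cycle tests, and an End of treatment visit may follow disclosure of progression, against the rule in footnote 9. Both are fair, and the fix has to deal with them.

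None of this covers patients stopped mid-cycle or before Cycle 2 Day 1, for whom no later report is scheduled, and 16.34 has no approach to missing booklets.

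**Conclusion.** The point holds in limited form. PRO state at discontinuation is collected only by chance of timing, and not at all by schedule for patients stopped between Day 1 visits. Patients off before Cycle 2 Day 1 contribute a baseline and nothing more. Mean changes at later cycles describe the patients who remained on treatment and would probably be too favourable if read as describing all treated patients.

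The number affected cannot be read from the documents; the counts in the working rest on assumed stopping rates and are illustrations. The effect is confined to goal 2.33 and leaves the two-stage design untouched. This is a cheap improvement, not a flaw in the trial's main inference.

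**What to change.** 1. **Section 4.0:** mark the booklet in the End of treatment column, unless one was already completed at that same visit. Have it completed before the response discussion where possible, and record when it was completed after.
2. **Sections 16.34 and 18.1:** align the timing to *baseline, every cycle and End of treatment*.
3. **Section 16.34, analysis:** add a change-from-baseline summary at End of treatment, since the by-cycle tests would otherwise leave the new booklet unused. Report booklet completion numbers by cycle, with reasons for missing booklets. Summarise Was It Worth It from each patient's last available booklet.

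The cost is one more booklet at a visit where exam, vitals and laboratory tests already take place: a few minutes of patient time. Some non-completion there must be expected, and the completion counts would show it. No sample size or decision rule changes.
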